APPENDIX B: PROGRAMMING MODIFIED NCI-CTCAE GRADING FOR LABORATORY ABNORMALITIES

Category	Analyte Name	CTCAE Term	Grade 1	Grade 2	Grade 3	Grade 4
Chemistry	Albumin	Hypoalbuminemia	<lower limit of normal (LLN) - 3 g/dL	<3 - 2 g/dL	<2 g/dL	-
Chemistry	Amylase	Serum amylase increased	>upper limit of normal (ULN) - 1.5 x ULN	>1.5 - 5.0 x ULN	>5.0 x ULN	-
Chemistry	Alanine Aminotransferase	Alanine aminotransferase increased	>ULN - 3.0 x ULN if baseline was normal; 1.5 - 3.0 x baseline if baseline was abnormal	>3.0 - 5.0 x ULN if baseline was normal; >3.0 - 5.0 x baseline if baseline was abnormal	>5.0 - 20.0 x ULN if baseline was normal; >5.0 - 20.0 x baseline if baseline was abnormal	>20.0 x ULN if baseline was normal; >20.0 x baseline if baseline was abnormal
Chemistry	Alkaline Phosphatase	Alkaline phosphatase increased	>ULN - 2.5 x ULN if baseline was normal; 2.0 - 2.5 x baseline if baseline was abnormal	>2.5 - 5.0 x ULN if baseline was normal; >2.5 - 5.0 x baseline if baseline was abnormal	>5.0 - 20.0 x ULN if baseline was normal; >5.0 - 20.0 x baseline if baseline was abnormal	>20.0 x ULN if baseline was normal; >20.0 x baseline if baseline was abnormal
Chemistry	Aspartate Aminotransferase	Aspartate aminotransferase increased	>ULN - 3.0 x ULN if baseline was normal; 1.5 - 3.0 x baseline if baseline was abnormal	>3.0 - 5.0 x ULN if baseline was normal; >3.0 - 5.0 x baseline if baseline was abnormal	>5.0 - 20.0 x ULN if baseline was normal; >5.0 - 20.0 x baseline if baseline was abnormal	>20.0 x ULN if baseline was normal; >20.0 x baseline if baseline was abnormal

Category	Analyte Name	CTCAE Term	Grade 1	Grade 2	Grade 3	Grade 4
			baseline was abnormal	if baseline was abnormal	if baseline was abnormal	baseline was abnormal
Chemistry	Bilirubin (Total or Direct)	Blood bilirubin increased	>ULN - 1.5 x ULN if baseline was normal; > 1.0 - 1.5 x baseline if baseline was abnormal	>1.5 - 3.0 x ULN if baseline was normal; >1.5 - 3.0 x baseline if baseline was abnormal	>3.0 - 10.0 x ULN if baseline was normal; >3.0 - 10.0 x baseline if baseline was abnormal	>10.0 x ULN
Chemistry	Calcium Corrected for Albumin	Hypocalcemia	<LLN - 8.0 mg/dL	<8.0 - 7.0 mg/dL	<7.0 - 6.0 mg/dL	<6.0 mg/dL
		Hypercalcemia	>ULN - 11.5 mg/dL	>11.5 - 12.5 mg/dL	>12.5 - 13.5 mg/dL	>13.5 mg/dL
Chemistry/ Lipid Profile	Cholesterol	Cholesterol high	>ULN - 300 mg/dL	>300 - 400 mg/dL	>400 - 500 mg/dL;	>500 mg/dL
Chemistry	Creatine Kinase	CPK increased	>ULN - 2.5 x ULN	>2.5 x ULN - 5 x ULN	>5 x ULN - 10 x ULN	>10 x ULN
Chemistry	Creatinine	Creatinine increased	>ULN - 1.5 x ULN	>1.5 - 3.0 x baseline or >1.5 - 3.0 x ULN	>3.0 x baseline or >3.0 - 6.0 x ULN	>6.0 x ULN

Category	Analyte Name	CTCAE Term	Grade 1	Grade 2	Grade 3	Grade 4
Chemistry	GGT	GGT increased	>ULN - 2.5 x ULN if baseline was normal; 2.0 - 2.5 x baseline if baseline was abnormal	>2.5 - 5.0 x ULN if baseline was normal; >2.5 - 5.0 x baseline if baseline was abnormal	>5.0 - 20.0 x ULN if baseline was normal; >5.0 - 20.0 x baseline if baseline was abnormal	>20.0 x ULN if baseline was normal; >20.0 x baseline if baseline was abnormal
Chemistry	eGFR or CrCL	eGFR decreased/CrCL decreased	<LLN - 60 ml/min/1.73 m2	<60 - 30 ml/min/1.73 m2	<30 - 15 ml/min/1.73 m2	<15 ml/min/1.73 m2
Chemistry	Glucose	Hypoglycemia	<LLN - 55 mg/dL	<55 - 40 mg/dL	<40 - 30 mg/dL	<30 mg/dL
Chemistry	Lipase	Serum lipase increased	>ULN - 1.5 x ULN	>1.5 - 5.0 x ULN	>5.0 x ULN	-
Chemistry	Magnesium	Hypermagnesemia	>ULN - 3.0 mg/dL	-	>3.0 - 8.0 mg/dL mmol/L	>8.0 mg/dL
		Hypomagnesemia	<LLN - 1.2 mg/dL	<1.2 - 0.9 mg/dL	<0.9 - 0.7 mg/dL	<0.7 mg/dL
Chemistry	Potassium	Hyperkalemia	>ULN - 5.5 mmol/L	>5.5 - 6.0 mmol/L	>6.0 - 7.0 mmol/L	>7.0 mmol/L
		Hypokalemia	<LLN - 3.0 mmol/L	-	<3.0 - 2.5 mmol/L	<2.5 mmol/L
	Sodium	Hypernatremia	>ULN - 150 mmol/L	>150 - 155 mmol/L;	>155 - 160 mmol/L	>160 mmol/L

Category	Analyte Name	CTCAE Term	Grade 1	Grade 2	Grade 3	Grade 4
Chemistry		Hyponatremia	<LLN - 130 mmol/L	125-129 mmol/L	120-124 mmol/L	<120 mmol/L
Chemistry/ Lipid Profile	Triglycerides	Hypertriglyceridemia	150 mg/dL - 300 mg/dL	>300 mg/dL - 500 mg/dL	>500 mg/dL - 1000 mg/dL	>1000 mg/dL
Chemistry	Uric Acid	Hyperuricemia	> ULN	-	-	-
Chemistry	Bicarbonate or CO2	Blood bicarbonate decreased	< LLN	-	-	-
Chemistry	Serum pH	Acidosis	pH <normal, but >=7.3	-	pH <7.3	-
		Alkalosis	pH >normal, but <=7.5	-	pH >7.5	-
Hematology	Hemoglobin	Anemia	<LLN - 10.0 g/dL; <LLN - 6.2 mmol/L; <LLN - 100 g/L	Hgb <10.0 - 8.0 g/dL; <6.2 - 4.9 mmol/L; <100 - 80g/L	Hgb <8.0 g/dL; <4.9 mmol/L; <80 g/L;	

Category	Analyte Name	CTCAE Term	Grade 1	Grade 2	Grade 3	Grade 4
Hematology	Lymphocytes	Lymphocyte count decreased	<LLN - 800/mm ³	<800 - 500/mm ³	<500 - 200/mm ³	<200/mm ³
		Lymphocyte count increased	-	>4000/mm ³ - 20,000/mm ³	>20,000/mm ³	-
Hematology	Neutrophils	Neutrophil count decreased	<LLN - 1500/mm ³	<1500 - 1000/mm ³	<1000 - 500/mm ³	<500/mm ³
Hematology	Platelets	Platelet count decreased	<LLN - 75,000/mm ³	<75,000 - 50,000/mm ³	<50,000 - 25,000/mm ³	<25,000/mm ³
Hematology	Leukocytes/White Blood Cells	Leukocytosis	-	-	>100,000/mm ³	-
Hematology	Leukocytes/White Blood Cells	White blood cell decreased	<LLN - 3000/mm ³	<3000 - 2000/mm ³	<2000 - 1000/mm ³	<1000/mm ³
Urinalysis	Urine Glucose	Glucosuria	Present	-	-	-
Urinalysis	Urine Protein	Proteinuria	1+ proteinuria	2+ and 3+ proteinuria	4+ proteinuria	-

Category	Analyte Name	CTCAE Term	Grade 1	Grade 2	Grade 3	Grade 4
Coagulation	Activated partial thromboplastin time	Activated partial thromboplastin time prolonged	>ULN - 1.5 x ULN	>1.5 - 2.5 x ULN	>2.5 x ULN	-
Coagulation	Fibrinogen	Fibrinogen decreased	<1.0 - 0.75 x LLN; if abnormal, <25% decrease from baseline	<0.75 - 0.5 x LLN; if abnormal, 25 - <50% decrease from baseline	<0.5 - 0.25 x LLN; if abnormal, 50 - <75% decrease from baseline	<0.25 x LLN; if abnormal, 75% decrease from baseline; absolute value <50 mg/dL
Coagulation	International Normalized Ratio	INR increased	>1.2 - 1.5	>1.5 - 2.5	>2.5	-

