### **2.5.3 Potential for Overlapping Toxicities Resulting from the Combination of LANRA and Gilteritinib**

In the reference safety information for LANRA, liver transaminase elevations are listed as potential adverse drug reactions, based on clinical trial experience to date. Transaminase elevations were infrequent and reversible upon discontinuation of LANRA. A review of the respective toxicity profiles for LANRA and gilteritinib reveals that the most likely overlapping and potentially treatment-limiting toxicity resulting from the combination is liver toxicity (ie, transaminase elevations). Other potential overlapping toxicities include (but are not limited to) rash, constitutional symptoms (fatigue/malaise, myalgia/arthralgia, fever, headache) and gastrointestinal signs/symptoms (nausea, vomiting, diarrhea, abdominal pain, constipation). These can be monitored by close surveillance and conventional safety assessments as described in [Section 11](#); all are potentially manageable with supportive care interventions and study treatment modifications ([Section 8](#)).

Co-administration with gilteritinib is not expected to impact LANRA plasma exposures. An evaluation of PK parameters for LANRA alone and in combination with gilteritinib will be conducted in this study to investigate the potential for meaningful PK interaction between the two.

In consideration of the above, the Sponsor has concluded that the potential benefits of the proposed study outweigh the risks for the following reasons:

- the prognosis for patients with R/R *FLT3*-mutated AML is dismal,
- there are limited effective treatment options available for this subgroup of patients,
- there is significant room for improvement when considering outcomes for patients treated with gilteritinib monotherapy in this clinical setting ([Section 2.2.1](#)),

- there is compelling evidence from non-clinical pharmacologic studies ([Puissant 2014](#)), as well as ex vivo pharmacodynamic studies of leukemic isolates from AML patients to suggest that incremental clinical benefit could be achieved from concurrent inhibition of SYK and FLT3,
- there is preliminary clinical evidence that the SYK inhibitor ENTO (the predecessor to LANRA) may improve CR rates when combined with standard “7 + 3” induction chemotherapy in newly diagnosed patients with *FLT3*-mutated AML ([Walker 2020](#)) and,

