### 8.1 Non-hematologic toxicities

#### 8.1.1 Gilteritinib

**Table 2: Treatment Modifications for Gilteritinib-Associated Toxicities**

Differentiation Syndrome (DS)*:	
 
• If DS is suspected, administer systemic corticosteroids (IV dexamethasone, 10 mg every 12 hours or equivalent) for a minimum of 3 days and initiate hemodynamic monitoring until symptom resolution.
 
• Interrupt gilteritinib if severe signs and/or symptoms persist for more than 48 hours after initiation of corticosteroids.
 
• Resume gilteritinib at full dose when signs and symptoms improve to Grade <math>\leq 2</math>.
 

Posterior reversible encephalopathy syndrome (PRES)**:	
 
• Discontinue gilteritinib.
 

QTcF interval greater than 500 msec:	
 
• Follow instructions provided in Section 11.7.3 regarding follow-up ECG assessments at the time of the event.
 
• Interrupt gilteritinib.
 
• Resume gilteritinib at 80 mg/day when QTcF interval returns to within 30 msec of baseline or <math>\leq 480</math> msec.
 

QTc interval increased by $>30$ msec on Day 8 of Cycle 1 compared to baseline:	
 
• Confirm with repeat ECG on Day 9.
 
• If confirmed, consider dose reduction to 80 mg/day.
 

Pancreatitis:	
 
• Interrupt gilteritinib until pancreatitis is resolved.
 
• Resume gilteritinib at 80 mg/day.
 

Liver function abnormalities:	
 
• For Grade 1-2 abnormalities, continue gilteritinib at full dose.
 
• For Grade <math>\geq 3</math> AST, ALT elevations interrupt gilteritinib and re-check
 

	
values at least weekly. If AST, ALT elevations resolve to Grade 1 or baseline in <math>\leq 14</math> days, re-start gilteritinib at 80 mg/day.
 
 
• Permanently discontinue gilteritinib for Grade <math>\geq 3</math> total bilirubin, interruptions lasting <math>> 14</math> days or recurrence of Grade <math>\geq 3</math> AST, ALT elevations despite dose reduction.
 

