**Table 4: Treatment Modifications for LANRA-Associated Toxicities**

Liver function abnormalities:	
 
For Grade 1-2 abnormalities, continue study treatment at assigned dose.
 
For Grade <math>\geq 3</math> AST, ALT withhold LANRA and re-check values at least weekly. If AST, ALT resolves to Grade <math>\leq 1</math> or baseline <math>\leq 14</math> days after interruption, re-start LANRA at dose level -1 (Table 3).
 
Permanently discontinue LANRA for interruption lasting <math>>14</math> days, Grade <math>\geq 3</math> total bilirubin or recurrence of Grade <math>\geq 3</math> AST, ALT elevations despite dose reduction.
 

Rash:	
 
For Grade 1-2 rashes that are clinically manageable with topical steroids, continue study treatment at assigned dose.
 
For Grade 3 rash, initiate treatment with topical steroids and interrupt LANRA until rash resolves to Grade <math>\leq 1</math>.
 
Re-start at dose level -1 if resolved <math>\leq 14</math> days of interruption (Table 3).
 
If Grade 3 rash does not recur after 2 weeks of reduced dose LANRA, escalation to full dose may be attempted at investigator's discretion.
 
Permanently discontinue LANRA in patients with Grade 4 rash, interruption for <math>>14</math> days or recurrent Grade 3 rash despite dose reduction.
 

Diarrhea:	
 
• For Grade 3 diarrhea, uncontrolled with anti-diarrheal medications, interrupt treatment until diarrhea resolves to Grade <math>\leq 1</math>.
 
• Re-start at dose level -1 if resolved after interruption lasting <math>\leq 14</math> days. (Table 3).
 
• Permanently discontinue LANRA for Grade 4 diarrhea, interruption lasting <math>>14</math> days or recurrence of Grade 3 diarrhea despite dose reduction.
 

Other non-hematologic toxicities related to LANRA†:	
 
• Interrupt LANRA until the toxicity resolves to Grade <math>\leq 1</math>, and then restart at dose level -1 (Table 3) if resolution occurs <math>\leq 14</math> days of interruption.
 
• Permanently discontinue LANRA for interruption lasting <math>>14</math> days or recurrence of Grade <math>\geq 3</math> toxicity despite dose reduction.
 

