ⁱ Includes electrolytes (sodium, potassium, chloride, total CO₂ and/or bicarbonate, calcium, phosphate, magnesium), liver function studies (aspartate aminotransferase [AST], alanine aminotransferase [ALT], total and direct bilirubin), albumin, lactate dehydrogenase (LDH), alkaline phosphatase, blood urea nitrogen or serum/plasma urea, creatinine, uric acid, glucose, creatine phosphokinase (CPK), amylase and lipase. Monitor electrolytes, liver function tests, blood urea nitrogen (BUN), creatinine, uric acid, and phosphate in accordance with institutional care standards until the risk of tumor lysis syndrome has abated. For patients receiving nephrotoxic antimicrobial agents, closer monitoring of renal function is recommended, consistent with institutional standards of care.

^j Includes dipstick evaluation for pH, glucose, protein, blood, and leukocyte esterase; conduct microscopic evaluation for red and white blood cells only if dipstick is abnormal. Perform urinalysis at Screening, and as clinically indicated during study treatment and thereafter if urine dipstick is abnormal.

^k Perform serum pregnancy test in WOCBP during Screening **within 7 days of C1D1**. Thereafter, perform urine β -hCG test at the beginning of each new cycle of study treatment and at End-of-Treatment. Repeat serum pregnancy test for confirmation of a positive urine β -hCG test result.

^m Perform bone marrow aspiration at Screening for morphology, karyotyping/FISH and biomarker assessments. A trephine bone marrow biopsy is required for patients in whom a satisfactory aspirate cannot be obtained (eg. due to dry tap, hypocellular or hemodiluted sample). Perform bone marrow aspiration (or biopsy) for response and biomarker assessments on Day 1 of Cycle 2 and Cycle 3 and every 3 cycles thereafter (ie.. Cycle 6, Cycle 9, etc.) until CR/CRh is documented on 2 consecutive bone marrow examinations. At other times, perform bone marrow examination for confirmation of suspected progression/relapse. Measurable residual disease will be assessed retrospectively in bone marrow aspirate (and peripheral blood concurrently) as an exploratory efficacy endpoint in patients who achieve CR or CRh. MRD assessments will be performed in a central testing facility designated by the Sponsor beginning with the 1st documented CR or CRh.

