6.6.3. Clinical Laboratory Assessments

Laboratory toxicities will be graded for severity using NCI-CTCAE Version 5.0 (see [Appendix B](#) for more details about laboratory grading). Frequencies and percentages of patients experiencing treatment-emergent grade 3 and 4 toxicities will be summarized.

Descriptive summaries of select quantitative clinical laboratory results (hemoglobin, white blood cells [WBC], absolute neutrophil count [ANC], platelets, blasts count, AST, ALT, alkaline phosphatase, amylase, lipase, total bilirubin, direct bilirubin, serum creatinine, urea nitrogen) and their changes from baseline will be presented by study visit.

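### SAP Appendix B grades total and direct bilirubin in one row under one term, so the Grade 3-4 bilirubin count can exceed what the protocol's total-bilirubin measure would give

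*SAP*

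**What the plan says.** The bilirubin row of SAP Appendix B names its analyte as "Bilirubin (Total or Direct" and assigns the single term "Blood bilirubin increased". Its Grade 3 cell reads ">3.0 - 10.0 x ULN if baseline was normal; >3.0 - 10.0 x baseline if baseline was abnormal"; Grade 4 is anything above 10 x ULN. The row does not say which ULN applies to direct bilirubin, or whether the two analytes are reported together.

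Both analytes are collected: the chemistry footnote in SAP 2.2 lists "total and direct bilirubin), albumin, lactate dehydrogenase (LDH" and others. SAP 6.6.3 sends laboratory grading to Appendix B and counts patients with treatment-emergent Grade 3 and 4 toxicities. SAP Section 10 lists one table for this, 14.3.2, and a chemistry toxicity listing, 16.2.8.2; neither names its selected analytes. For the by-visit quantitative summaries, 6.6.3 treats the two as separate analytes: "total bilirubin, direct bilirubin, serum creatinine, urea nitrogen".

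The protocol uses total bilirubin throughout. Inclusion criterion 5 requires total bilirubin below 1.5 x ULN, with an exception for Gilbert's Disease or hemolysis. Table 2 permanently stops gilteritinib for Grade 3 or higher "total bilirubin, interruptions lasting" more than 14 days, or recurrent transaminase elevation. Table 4 permanently stops LANRA on a list that includes Grade 3 or higher "total bilirubin or recurrence of Grade" 3 or higher AST or ALT elevation.

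**The concern.** Direct bilirubin is a fraction of total and normally has a much lower ULN. The same multiple of ULN is therefore reached at a smaller absolute value. Read literally, the row lets either analyte set the grade of one shared term. A patient who is Grade 1 or 2 on the protocol's measure could then be tabulated as Grade 3 because of the direct fraction.

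Safety is the Phase 1b primary objective, and under SAP Section 7 only Phase 1b is analysed. Dose groups start at 3 to 6 patients and may reach 20, so one reclassified patient moves a group's rate by 1/3 = 33, 1/6 = 17 or 1/20 = 5 percentage points. A Grade 3 bilirubin in the table for a patient who never reached Grade 3 on total bilirubin could also look like a missed discontinuation under Table 2 or 4.

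**Working it through.** **Inputs from the documents.** For a normal baseline, Appendix B gives Grade 1 up to 1.5 x ULN, Grade 2 up to 3 x ULN, Grade 3 up to 10 x ULN and Grade 4 above that. The plan states no figure on this point to reproduce.

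**Assumptions.** The documents give no ULNs. I take total ULN 1.0-1.3 mg/dL and direct ULN 0.2-0.5 mg/dL. Both baselines are normal, direct cannot exceed total, and direct is graded against its own ULN.

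**Which ULN.** If direct were graded against the total ULN it could never exceed the total grade, and including it would change nothing. With a normal baseline, its inclusion matters only if direct has its own, lower limit.

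**Formula.** Let R = total ULN / direct ULN. If total is at most k x its ULN, direct can be at most k x R times the direct ULN.

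- Direct Grade 3 with total Grade 2 (k = 3): 3R > 3, so R > 1.
- Direct Grade 3 with total Grade 1 (k = 1.5): 1.5R > 3, so R > 2.
- Direct Grade 4 with total Grade 2: 3R > 10, so R > 3.33.
- Direct Grade 4 with total Grade 1: 1.5R > 10, so R > 6.67.

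The assumed range is R = 1.0/0.5 = 2.0 to 1.3/0.2 = 6.5. Grade 3 from total Grade 2 is reachable throughout. Grade 3 from total Grade 1 is reachable everywhere except at R = 2.0. Grade 4 from total Grade 1 is reachable nowhere.

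**Direct share of total that must be exceeded**, with total at the top of its grade:

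| Total / direct ULN (mg/dL) | R | Total G2 to direct G3 (1/R) | Total G1 to direct G3 (2/R) | Total G2 to direct G4 (10/(3R)) |
|---|---|---|---|---|
| 1.0 / 0.5 | 2.0 | 50% | not reachable | not reachable |
| 1.2 / 0.4 | 3.0 | 33% | 67% | not reachable |
| 1.2 / 0.3 | 4.0 | 25% | 50% | 83% |
| 1.3 / 0.2 | 6.5 | 15% | 31% | 51% |

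**Examples with total ULN 1.2 mg/dL.**

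- Total 2.4 is 2.4/1.2 = 2.0 x ULN, Grade 2. Direct 1.7 is 1.7/0.5 = 3.4 to 1.7/0.2 = 8.5 x ULN, Grade 3 at every assumed direct ULN.
- Total 1.8 is 1.5 x ULN, Grade 1. Direct 1.26 (70% of total) with direct ULN 0.3 is 4.2 x ULN, Grade 3.
- Total 3.5 is 2.9 x ULN, Grade 2. Direct 3.1 is 15.5 or 10.3 x ULN at direct ULN 0.2 or 0.3 (Grade 4), and 7.75 or 6.2 x at 0.4 or 0.5 (Grade 3).

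**Abnormal baseline.** Grades 1-3 are then multiples of the patient's own baseline. If both baselines are abnormal and both analytes rise in proportion, they receive the same Grade 1-3 result. The ULN argument above therefore covers normal baselines only.

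**The case against.** The strongest objection is that pooling is inferred. Nothing says total and direct are collapsed to one worst grade per patient. Other Appendix B rows pair analytes in the same way (eGFR with CrCL, bicarbonate with CO2), so the label might mean only that each is graded with the same cut points. SAP 6.6.3 lists the two bilirubins separately, and the selected analytes of Table 14.3.2 are not named. On separate lines, the total-bilirubin count would not change. This stands, so the count *can* be inflated; it is not shown that it will be. It does not rescue the row. The other pairs are alternative measures of one quantity, which direct and total bilirubin are not. Both also carry the same term, and independent programmers, whom SAP Appendix A requires, could code the row differently. The separate by-visit summaries would help a reader, but SAP Section 10 lists no table for them.

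A reader might also infer that the row distorts the trial's main named risk, since Protocol 2.5.3 says "the most likely overlapping and potentially treatment-limiting toxicity resulting from the combination is liver toxicity". That sentence goes on to define the toxicity as transaminase elevations. AST and ALT have their own Appendix B rows, which this point does not touch.

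Finally, no decision depends on the row. DLTs rest on toxicities graded by CTCAE v5.0 (Protocol Appendix 1), the modification tables name total bilirubin, and the SAP states no formal hypothesis. All of that stands and limits the point to descriptive laboratory outputs.

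**Conclusion.** The row is wrong as written, with minor severity. It puts two analytes with different limits under one term and one set of multiples, and departs from the total-bilirubin measure that the protocol uses everywhere.

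If direct is graded on its own ULN and counted under the shared term, a normal-baseline patient with Grade 2 total bilirubin can be counted as Grade 3. So can one with Grade 1 total where R exceeds 2. The size depends on the assumed ULNs, on the direct share in each patient, and on bilirubin being among the selected analytes. The documents settle none of these.

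It would be too strong to say that Grade 1-2 total generally becomes Grade 3-4: Grade 4 arises only from total Grade 2, with R above 3.33, and from total Grade 1 at no assumed pair of limits. Nor do the documents support any effect on DLTs, discontinuation rules or the transaminase results.

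**What to change.** In SAP Appendix B, restrict the graded "Blood bilirubin increased" row to total bilirubin, and keep direct bilirubin as the quantitative summary already planned in SAP 6.6.3. If direct is to be graded, state its limit and give it a separately labelled line that does not count toward the shared term.

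The first option costs a short deletion in the row label and one programming condition; the second adds a row and a label. Under either, the Grade 3-4 count for the term can only fall or stay the same. No clinical rule changes and no new data are needed.
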